## **2. Objectives (include all primary and secondary objectives)**

Specific Aim 1: To test whether nasal CPAP reduces the incidence of hypoxia during procedural sedation with propofol as compared to usual care. Hypothesis: A randomized clinical trial of an intervention to reduce airway obstruction (nasal CPAP) will decrease the incidence of hypoxic events ( $<90\% \geq 15s$ ) compared to usual care in patients undergoing procedural sedation.

Specific Aim 2: To determine the duration, magnitude and mechanism of hypoventilation and its association with hypoxia in subjects undergoing procedural sedation. Hypothesis: By determining minute ventilation, transcutaneous CO2 and sedation depth while measuring end-tidal CO2, it will be possible to relate ventilation to hypoxic events, sedation depth and airway obstruction. Further, reductions in the incidence of hypoxia in the intervention group will be consistent with the hypothesis that loss of airway motor tone underlies hypoventilation and associated hypoxia.

Specific Aim 3: To characterize the physiologic state when end-tidal capnography is insufficient for detecting hypoventilation. Hypothesis: The amplitude of the capnographic signal is not representative of the adequacy of ventilation due to artifact from loss of airway motor tone during procedural sedation.

Specific Aim 4: To determine if there short chain fatty acid serum concentration is protective for procedural sedation induced hypoventilation, obstruction and hypoxia: Hypothesis: Higher concentration

of short chain fatty acids will be reduce the risk of hypoventilation, obstruction, and hypoxia and suggests a link between respiratory function and gut microbiome.

**3. Background** (briefly describe pre-clinical and clinical data, current experience with procedures, drug or device, and any other relevant information to justify the research)

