Hypoxia is related to both centrally mediated changes in respiratory drive caused by sedative drugs, direct effects of the anesthetic agents on motor function, and diminished airway tone due to sleep or sedation (change in state). Furthermore, sedative agents decrease airway tone and increase the risk of obstruction, while blunting the normal arousal that occurs in response to hypercarbia and hypoxia during obstruction events during natural sleep. Obstructive sleep apnea and obesity are risk factors for airway obstruction during sedation. Use of nasal CPAP has been demonstrated to improve ventilation, alleviate upper airway obstruction, and reverse hypoxia in women undergoing spinal anesthesia with sedation for gynecological procedures. Continuous positive pressure stents the airway, alleviating the obstruction from oropharyngeal soft tissue that occurs during sleep and under sedation, and has been advocated in patients with obstructive sleep apnea on CPAP at home. Positive pressure ventilation using a nasal mask has also been shown to be effective. The Supernova mask (RMD medical, Tucson, AZ) is FDA approved commercially available nasal mask that can be attached to a standard anesthesia circuit or Jackson Reese, and allows for up to 30 l/min of oxygen delivery, making it convenient for use in procedural sedation. It can supply CPAP as well as supplemental positive pressure breaths by closing the mouth or applying gentle cephalad directed submandibular pressure to push close the oropharynx by approximation of the tongue and palate.

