#### **4. Study Procedures**

Study design, including the sequence and timing of study procedures (distinguish research procedures from those that are part of routine care).

This study is a randomized controlled trial comparing oxygen delivery with nasal CPAP versus standard care (delivery via nasal cannula or standard facemask) during propofol-based sedation for endoscopic procedures. The primary outcome will be the rate of oxygen desaturation below 90% for  $\geq 15$  seconds. Secondary outcomes are the degree of hypoventilation measured by continuous transcutaneous carbon dioxide (TcCO2), the change in minute ventilation (MV) and obstructive episodes measured by impedance-based respiratory volume monitoring, and depth of anesthesia measured by bispectral index (BIS) monitoring. The adequacy of standard ETCO2 monitoring will also be assessed. In addition, all clinical data utilized in routine practice will be recorded, including drug dosing, method of drug administration, blood pressure changes, frequency of interruption of procedure for airway maneuvers or rescue, length of stay in the recovery area, and any complications that are identified.

Subjects will be recruited from the patient population scheduled for MAC with sedation for gastrointestinal endoscopic procedures at the Johns Hopkins Hospital Endoscopy Center on Zayed 2. Patients scheduled for colonoscopy, EGD (including EGD with biopsy, ultrasound, PEG

placement, or enteroscopy ) or combined upper and lower endoscopic procedures predicted to last longer than 10 minutes and for which MAC with sedation is the planned anesthetic technique will

Page 5 of 12

be considered for the study. A study team member will screen the endoscopy schedule for potential subjects. We will direct our recruitment to patients with documented OSA or a BMI  $\geq 30$ , but we not limit it to just those patients. Written, informed consent will be obtained from interested eligible subjects or their representative.

As part of routine care, all patients undergoing MAC with sedation receive an IV in the preoperative area. During the placement of this IV up to 15 mL of blood will be collected for short chain fatty acids measurements and possibly the measurement of biomarkers and other compounds. The written consent form will include permission from the participant to store their blood for future research.

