All subjects will also have standard, routine monitors placed by the treating team, including blood pressure, ECG, pulse oximetry, and EtCO2. Subjects will be randomized to either 1) receive oxygen by nasal mask (nCPAP) with CPAP of 10 mmHg or 2) standard oxygen therapy. Subjects randomized to nCPAP will have a nasal facemask (SuperNOVA) placed approximately 5 minutes prior to the procedural start. The mask attaches to the anesthesia circuit, oxygen flow will be set at 10 lpm, and the CPAP of 10 will be set by turning the "pop-off" valve to 10 mmHg. Subjects randomized to standard care will have oxygen delivered by nasal cannula or simple facemask with oxygen level set by the treating providers. The CPAP level of 10 will be chosen because previous studies suggest that 95% of airway obstruction can be alleviated with a CPAP of 7.1, and it is convenient marked on the anesthesia "pop-off" valve, ensuring standardization. For the CPAP group, flow below 10 lpm will be allowed in cases in which the patient or provider does not tolerate higher flows. For practicality, providers and patients will not be blinded to the intervention because application of the nasal mask is obvious. While the clinical team will have access to all of the routine monitors, they will be blinded to the research monitor data, which will include TcCO2 monitoring, respiratory volume monitoring (RVM), and BIS. Researchers analyzing the data will be blinded to the intervention.

All subjects will receive a routine propofol-based anesthetic per the treating clinical team. A study team member will record all airway maneuvers or interventions performed by the anesthesia team during the procedure, including changes in oxygen flow, ventilatory assistance, jaw thrust, or placement of an oral or nasal airway. Further, the duration of the endoscopic procedure and any anesthesia related interruptions will be recorded. The study duration will be entirely within the time period of the patients' visit to the endoscopy suite. All study monitors will be removed when the participants are discharged to home or transferred to the ward depending on the clinical routine or needs.

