## 7. Study Statistics

### a. Primary outcome variable.

The primary outcome will be the rate of hypoxia below 90% for  $\geq 15$  seconds.

- ### b. Secondary outcome variables. Secondary outcomes will include change in respiratory parameters (tidal volume, respiratory rate, minute ventilation, obstructive events), hypoventilation by TcCO2, EtCO2, and depth of anesthesia by BIS, as well as demographic differences. Demographic information to the occurrence of hypoxic events will be analyzed with logistic regression.

Statistical plan including sample size justification and interim data analysis.

Power analysis is based on a previous German study in the literature, of patients undergoing upper and lower endoscopy with hypoxia rates of 13.5% with standard care and 1.8% with application of nasopharyngeal airway. Using these figures to perform a power analysis for the primary outcome of hypoxia below 90%, with alpha 0.05 and power of 0.9, approximately 109 subjects in each arm or a total of 218 subjects will be needed. In order to obtain 109 completed subjects in each arm and to allow for those participants with incomplete datasets (e.g. monitor failure), we will enroll 120 subjects in each arm and a total of 240 subjects.

Frequency data will be analyzed with Fisher's Exact Test, ordered categorical data will be analyzed with the rank sum test, and continuous data will be analyzed with regression or equivalent techniques. Therefore, our primary outcome as to the incidence of hypoxia in each arm of the study will be determined using Fisher's exact test. All time series data from multiple sources will be aligned using the associated time stamp with the aid of the program data manipulation capabilities in Mathematica 11. Longitudinal analysis will be performed using a mixed model approach, initially with random intercepts alone, with the addition of nonlinear terms and interaction as indicated by the resulting model. Throughout, findings will be considered significant for  $p < 0.05$  and  $p$  values will be determined using two-sided tests. Statistical analysis will be performed with the aid of Stata 13. An analysis will be performed after the first 20 subjects to ensure complete data collection and to run a batched analysis of SCFA to evaluate this aim. An interim data analysis will be done after ~120 subjects have been enrolled.

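### Recruitment targets documented OSA or BMI ≥30, but no stratification by that factor is specified and no arm comparison is stated to adjust for it

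*Combined protocol and SAP*

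**What the plan says.** Aim 1 (section 2) is stated for procedural sedation in general: "To test whether nasal CPAP reduces the incidence of hypoxia during procedural sedation with propofol as compared to usual care". Section 5 admits adults having upper, lower or combined endoscopy and sets no OSA or BMI criterion. Section 4 then steers enrolment: "We will direct our recruitment to patients with documented OSA or a BMI" of at least 30. It adds that others may also enter, and gives no quota or target share.

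The background (section 3) gives the reason this factor matters: "Obstructive sleep apnea and obesity are risk factors for airway obstruction during sedation". It also reports that higher BMI went with more sedation-related adverse events in a cited cohort.

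On allocation, section 4 says only: "Subjects will be randomized to either 1) receive oxygen by nasal mask (nCPAP) with CPAP of 10 mmHg or 2) standard oxygen therapy". The protocol does not describe a sequence method, blocking, concealment or stratification.

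Section 7 makes Fisher's exact test the primary analysis. Continuous outcomes go to regression or equivalent techniques, and longitudinal data to mixed models. Logistic regression will relate demographic information to hypoxic events. None of these models is said to include OSA, BMI group or treatment arm. An interim analysis is planned after about 120 subjects, with stopping considered for clear benefit or clear lack of it.

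**The concern.** The protocol picks out one patient characteristic, aims recruitment at it, and explains why it should raise the risk of the event that the intervention targets. It then does nothing stated to balance the arms on it or to use it in comparing them. With few hypoxia events, a reader of the baseline table could reasonably ask whether a difference between arms reflects the mask or the mix.

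Two things are at stake. The first is precision and credibility in the secondary comparisons (minute ventilation, obstruction, TcCO2), where a prognostic factor left out of the model adds avoidable variance. The second is interpretation. Aim 1 speaks of sedation patients generally, the sample is deliberately tilted, and no result by arm is planned within the group that recruitment favours. Stratified allocation is also the one part of the remedy that cannot be added once patients have been randomised.

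**Working it through.** **1. The plan's own sample size.** Inputs from section 7: "hypoxia rates of 13.5% with standard care and 1.8% with application of nasopharyngeal airway"; "with alpha 0.05 and power of 0.9, approximately 109 subjects in each arm or a total of 218 subjects will be needed"; "values will be determined using two-sided tests"; and "we will enroll 120 subjects in each arm and a total of 240 subjects". The usual two-proportion formula with pooled variance under the null and no continuity correction gives 107 per arm. The exact power of Fisher's test at 109 per arm is 90.8%. The stated 109 is therefore reproduced. (Section 3 lists the two planning rates in the opposite order. That is a separate matter to reconcile; section 7's order is used here.)

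**2. Expected events.** At 109 per arm: 109 × 0.135 = 14.7 in control and 109 × 0.018 = 2.0 on CPAP, about 17 in all. At 60 per arm: 60 × (0.135 + 0.018) ≈ 9.

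**3. Chance of imbalance under simple randomisation.** The share q with documented OSA or BMI ≥30 is not given, so 50–70% is assumed. The number of such patients in each arm is taken as binomial(n, q), and the probability that the two arms' shares differ by at least the stated amount is computed exactly.

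| n per arm | q | ≥10 points | ≥15 points |
|---|---|---|---|
| 120 | 0.5 | 13.8% | 2.4% |
| 120 | 0.6 | 13.0% | 2.1% |
| 120 | 0.7 | 10.5% | 1.4% |
| 60 | 0.5 | 31.5% | 12.0% |
| 60 | 0.6 | 30.5% | 11.3% |
| 60 | 0.7 | 27.3% | 9.0% |

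**4. What an imbalance does to the primary result.** The only rates by risk group in the documents are in section 3: 16.9% hypoxia with a STOP-BANG score above 3 and 11.2% below 3, a difference reported as not significant. They are a proxy, since the score is neither documented OSA nor BMI. Shift in the risk difference = imbalance × (high-risk rate − low-risk rate):

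- 10 points: 0.10 × 5.7 = 0.57 points
- 13.3 points (95% limit at 109 per arm and q = 0.5, from 1.96 × √(2 × 0.5 × 0.5/109)): 0.76 points
- 15 points: 0.15 × 5.7 = 0.86 points

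The planned difference is 13.5 − 1.8 = 11.7 points. With a much stronger assumed factor (22% against 5%), the 13.3-point imbalance gives 0.133 × 17 = 2.3 points.

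**5. Simple against stratified allocation, Fisher's test unchanged.** Simulation with 20,000 runs, 109 per arm, q = 0.5 and the planned risk ratio 1.8/13.5 = 0.133:

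| Risk by group | Power, simple | Power, stratified | Type I, simple | Type I, stratified |
|---|---|---|---|---|
| 16.9% / 11.2% | 92.2% | 91.8% | 3.0% | 2.9% |
| 22% / 5% (assumed) | 90.7% | 91.3% | 3.3% | 2.6% |

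At the proxy rates the standard error of the risk difference is about 0.036 with either allocation.

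**6. Gain in continuous secondary outcomes.** If the factor shifts an outcome by d within-group standard deviations, adjusting for it removes a fraction d²q(1 − q) / [1 + d²q(1 − q)] of the variance. With q = 0.5, an assumed d = 0.3 gives 0.0225/1.0225 = 2.2%, and d = 0.8 gives 0.16/1.16 = 13.8%.

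**7. Case mix.** At the proxy rates the control rate would be 11.2% with no high-risk patients, 14.1% with half and 16.9% with all. At the planned risk ratio, power at 109 per arm is then 84%, 92% and 96%.

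**The case against.** The strongest reply is that randomisation already deals with this. Chance imbalance is not bias, Fisher's test allows for it, and steps 4 and 5 show almost no effect on the primary comparison. That stands, and it disposes of a reading that is easy to slip into: that imbalance would confuse the primary result. The documents' figures do not support that.

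Directed recruitment is openly stated and, if it raises the event rate, helps power (step 7). That also stands. The limit on generalising is a matter of how the conclusion is worded.

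Section 7 does plan a logistic regression on demographic information, and section 4 links clinical characteristics to the physiological data. This helps in part, but the regression is secondary and names neither the factor nor treatment arm.

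Subgroup results would rest on about 17 events, about 2 of them on CPAP. They cannot show whether CPAP works in either group, so they should be descriptive only.

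A reader might also want procedure route as a second stratification factor, because section 3 mentions closing the mouth to deliver pressure. The same sentence offers submandibular pressure as an alternative, and the protocol nowhere names route as a risk factor for hypoxia and gives no rates by route. That extension is not supported.

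Finally, the documents are silent on the randomisation method. It is fair to say that no stratification is specified, but not that the sponsor chose an unstratified design.

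**Conclusion.** The point holds as a worthwhile improvement, not as a threat to the primary analysis. The plan targets one prognostic factor in recruitment and states no use of it in allocation or in comparing the arms. Under simple randomisation, an imbalance of at least 10 points has a chance of about 10–14% in the full trial and 27–32% with 60 per arm, roughly the interim. Its effect on the primary risk difference is under 1 point at the proxy rates and about 2 points under a deliberately strong assumption, against 11.7 planned. Adjusting the continuous secondary outcomes would remove about 2–14% of their variance.

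These sizes rest on an assumed 50–70% share (50% for the variance figure), a non-significant proxy for risk by group, and assumed effects of 0.3–0.8 SD.

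A reader might infer that stratifying would also control the overall case mix. It would not: it balances the arms, while the share enrolled still depends on who is approached. Only the wording of the Aim 1 conclusion addresses that.

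**What to change.** **Section 4:** state that subjects are randomised 1:1 in permuted blocks, stratified by documented OSA or BMI ≥30 (yes/no).

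**Section 7:** keep Fisher's exact test as the primary analysis. Include the stratification factor together with treatment arm in the secondary regressions for minute ventilation, obstruction and TcCO2, and in the logistic model for hypoxia. Report hypoxia by arm within each level of the factor, labelled descriptive. State the Aim 1 conclusion for the mix actually enrolled, giving the share with the factor.

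**Cost:** no extra patients or procedures, and the planned sample size is essentially unchanged. The factor must be read from the chart and entered before allocation, and the list is stratified rather than simple. The gain for the primary comparison is small and should not be oversold.

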## 5. Inclusion/Exclusion Criteria Inclusion Criteria

Adult patients ( $\geq 18$  years of age) undergoing colonoscopy, EGD, EGD with biopsy and/or ultrasound, or combined upper and lower endoscopy procedure anticipated to last longer than 10 minutes in the Endoscopy Suite in the Sheikh Zayed Tower at the Johns Hopkins Hospital when the anesthetic plan is MAC with propofol-based anesthesia with a natural airway.

### Exclusion Criteria

LVAD

Severe Pulmonary Hypertension (defined by the PI or co-investigators during the screening)

EF < 35%

Active CHF

Planned procedure is Balloon Enteroscopy, ERCP

Topical lidocaine administration

Pregnancy

Previous enrollment in this study

## 6. Drugs/ Substances/ Devices

a. The rationale for choosing the drug and dose or for choosing the device to be used.

The ExSpiron™ is an FDA-approved device that allows acquisition of quantitative values of minute ventilation (MV) (Respiratory Motion, Inc. Waltham). Unlike currently utilized ECG derived RR, the device's detection algorithm has been tuned to identify not just the onset of a new breath (RR) but also to estimate the thoracic size changes to provide a measurement of TV.

Transcutaneous CO2 (Ptc CO2) monitoring provides a noninvasive technique allowing continuous monitoring of ventilation. It is based on arterIALIZATION of the capillary bed through the local application of heat and the use of Stow-Severinghaus electrodes. Transcutaneous CO2 monitors have been used in patients as young as neonates and a good correlation between Ptc CO2 and PaCO2 has been found in adults and children. (Berkenbosch JW, Tobias JD. Crit Care Med 2002 30:1024–1027. Herrejo'n A, Inchaurrega I, et al. Arch Bronconeumol 2006 42:225–229). The BIS monitor is an FDA approved, noninvasive monitor that can provide a validated monitor for depth of anesthesia and sedation.

The SuperNova™ is an FDA approved nasal anesthesia mask that can generate CPAP to maintain airway patency, provide ventilator support, and provide rescue nasal ventilation during procedural sedation and during the perioperative period. The most likely risk is a red mark on the face from the mask, dry nose and mouth, and the very unlikely risk of nose bleed. (In fact, a common rescue during standard therapy is to place a nasopharyngeal airway, which carries a higher risk of nose bleed). CPAP and ventilator interventions associated with the nasal mask carry similar risks to interventions that may be required in patients undergoing sedation who require additional ventilator support.

b. Justification and safety information if FDA approved drugs will be administered for non-FDA approved indications or if doses or routes of administration or participant populations are changed. Not applicable

c. Justification and safety information if non-FDA approved drugs without an IND will be administered. Not applicable

## 7. Study Statistics

### a. Primary outcome variable.

The primary outcome will be the rate of hypoxia below 90% for  $\geq 15$  seconds.

- ### b. Secondary outcome variables. Secondary outcomes will include change in respiratory parameters (tidal volume, respiratory rate, minute ventilation, obstructive events), hypoventilation by TcCO2, EtCO2, and depth of anesthesia by BIS, as well as demographic differences. Demographic information to the occurrence of hypoxic events will be analyzed with logistic regression.

Statistical plan including sample size justification and interim data analysis.

Power analysis is based on a previous German study in the literature, of patients undergoing upper and lower endoscopy with hypoxia rates of 13.5% with standard care and 1.8% with application of nasopharyngeal airway. Using these figures to perform a power analysis for the primary outcome of hypoxia below 90%, with alpha 0.05 and power of 0.9, approximately 109 subjects in each arm or a total of 218 subjects will be needed. In order to obtain 109 completed subjects in each arm and to allow for those participants with incomplete datasets (e.g. monitor failure), we will enroll 120 subjects in each arm and a total of 240 subjects.

Frequency data will be analyzed with Fisher's Exact Test, ordered categorical data will be analyzed with the rank sum test, and continuous data will be analyzed with regression or equivalent techniques. Therefore, our primary outcome as to the incidence of hypoxia in each arm of the study will be determined using Fisher's exact test. All time series data from multiple sources will be aligned using the associated time stamp with the aid of the program data manipulation capabilities in Mathematica 11. Longitudinal analysis will be performed using a mixed model approach, initially with random intercepts alone, with the addition of nonlinear terms and interaction as indicated by the resulting model. Throughout, findings will be considered significant for  $p < 0.05$  and  $p$  values will be determined using two-sided tests. Statistical analysis will be performed with the aid of Stata 13. An analysis will be performed after the first 20 subjects to ensure complete data collection and to run a batched analysis of SCFA to evaluate this aim. An interim data analysis will be done after ~120 subjects have been enrolled.

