The large and growing number of GE procedures with anesthesia services underlies the importance of delivering safe care, as even a low rate of sedation related adverse events may affect a large number of patients. In several retrospective studies, cardiopulmonary events occurred in up to 11.7/1000 events, and hypoxia was the most common. While the full implication of mild transient hypoxia on outcomes is unknown, significant hypoventilation with hypercarbia and hypoxia commonly proceeds cardiopulmonary arrest. Respiratory depression from oversedation is an important mechanism of patient injury during monitored anesthesia care. The rate of hypoxia is considered as a marker for unsafe sedation practices in endoscopy suites. However, the true rate of hypoxia associated with sedation for endoscopic procedures is unknown and ranges from 1% to 70% in the literature. The variability may be related to adequacy of surveillance as well as differences in the definition of hypoxia. For instance, lower rates of hypoxia in manually and electronically recorded pulse oximetry data during clinical care have been reported. A recent study from the Netherlands reported a hypoxia rate in average risk patients during sedation for colonoscopy without oxygen supplementation of 55.6%. A recent study from Germany pseudorandomized patients undergoing upper, lower, or combined endoscopic procedures with propofolbased anesthesia to nasal cannula alone or with a nasopharyngeal airway and found rates of

hypoxia of 1.8% versus 13.5%. In another study from the Cleveland Clinic evaluating the STOP-BANG sleep apnea scoring system, subjects with STOP-BANG score >3 had a rate of hypoxia of 16.9% versus 11.2% in the STOP-BANG score <3 group, but this did not reach significance in this underpowered study. However, higher BMI was associated with more sedation-related adverse events (SRAE).

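### The demographic logistic regression of hypoxia rests on about 17 expected events; Firth penalised likelihood would be a cheap safeguard against sparse categories and imprecise odds ratios

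*Combined protocol and SAP*

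**What the plan says.** Section 7 (Study Statistics), item b, lists the secondary outcomes and adds: "Demographic information to the occurrence of hypoxic events will be analyzed with logistic regression". Nothing further defines this model. The section does not name the demographic factors or limit their number. It does not say whether they are examined singly or jointly, or whether arm is included. No penalised or exact version of the regression is mentioned.

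The outcome is a low-frequency binary event. The sample size assumes "hypoxia rates of 13.5% with standard care and 1.8% with application of nasopharyngeal airway" and concludes that "with alpha 0.05 and power of 0.9, approximately 109 subjects in each arm or a total of 218 subjects will be needed". To allow for incomplete datasets, "we will enroll 120 subjects in each arm and a total of 240 subjects".

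The treatment comparison is handled separately: "our primary outcome as to the incidence of hypoxia in each arm of the study will be determined using Fisher's exact test".

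**The concern.** With a binary outcome, the information in a logistic model is governed by the number of events, not the number of patients. If the intervention works as assumed, almost all events fall in one arm and the total is small. Maximum likelihood then has three weaknesses. Odds ratios are imprecise. They tend to lie somewhat too far from 1. The fit has no finite solution if some level of a predictor contains no events.

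The plan gives no rule for that last case. The analyst would have to merge categories or drop terms after seeing the data, in an analysis judged at the same two-sided p < 0.05 as the rest. What is at stake is the reliability of a secondary, descriptive analysis of who becomes hypoxic. The treatment effect is not at stake.

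**Working it through.** **Inputs (Section 7).** Rates 13.5% and 1.8%; 109 completed and 120 enrolled per arm; two-sided alpha 0.05; power 0.90; Fisher's exact test.

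**Reproducing the plan's sample size.** Two-proportion formula with pooled variance under the null, mean rate (0.135 + 0.018)/2 = 0.0765:

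n = [1.960 × √(2 × 0.0765 × 0.9235) + 1.2816 × √(0.135 × 0.865 + 0.018 × 0.982)]² / 0.117² = (0.737 + 0.470)² / 0.01369, which rounds up to 107 per arm.

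This is within 2 of the stated 109. Exact Fisher power at 109 per arm is 0.908. The planning figures are therefore coherent and can be used for the event count.

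**Expected events.**
- 109 per arm: 109 × 0.135 + 109 × 0.018 = 14.7 + 2.0 = 16.7 (central 95% range 10 to 25).
- 120 per arm: 16.2 + 2.2 = 18.4 (range 11 to 27).
- Stopping at the midpoint, which item c of Section 7 allows, with 60 per arm: 60 × 0.153 = 9.2.

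**Events per model term at 16.7 events.** Two terms, 8.3; three, 5.6; four, 4.2; five, 3.3.

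**Chance of no events in the CPAP arm.** 0.982^109 = 13.8%; 0.982^120 = 11.3%.

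**How often maximum likelihood fails.** This was simulated with 3,000 trials per setting at 109 per arm. The covariates are assumptions, because the plan lists none: standardised age and BMI, sex 50%, OSA 30%, and optionally one category of 10% prevalence. The true odds ratio was 2 per SD of BMI and 2 for OSA, with event rates set to 13.5% and 1.8%. A fit counted as failed if it broke down or diverged.

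| Model | Failed fits |
|---|---|
| Four demographics, no arm | 0.1% |
| Four demographics plus arm | 13% |
| Four demographics plus 10%-prevalence category, no arm | 18% |
| Both added | 29% |

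Runs of 2,000 trials with six demographic factors and smaller assumed effects (log odds ratio 0.4 per SD of BMI, 0.5 for OSA, others 0) gave 0.1% to 0.5% failures without arm and about 13% to 15% with arm. In one such run with arm, 12.65% of fits failed, and trials with no CPAP-arm events accounted for 12.55%. In those trials the arm coefficient goes to minus infinity and the CPAP arm drops out of the likelihood. The demographic coefficients are then estimated from the control arm, and they remained finite in 99.9% of trials.

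**Quality of the fits that succeed.**
- *Precision.* With four demographics and no arm, the standard error of the BMI coefficient is about 0.283. The upper 95% limit is therefore exp(2 × 1.96 × 0.283) = 3.0 times the lower. BMI is the best-estimated term.
- *Without arm.* With six demographics the mean BMI coefficient was 0.391 against a true 0.40, with 95.3% coverage.
- *With arm.* The BMI coefficient was about 7% to 9% too large. On a log odds ratio of 0.4, 9% is 0.036: an odds ratio of 1.49 becomes 1.55, against a standard error near 0.29. Coverage stayed near 95%.

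**Firth with the same terms.** Every trial gave a finite estimate. With arm and six demographics, the BMI coefficient was about 1% to 2% too small, and root mean square error for OSA fell from 0.64 to 0.58, which is 0.06/0.64 = 9%. Across the configurations tried the reduction was about 3% to 12%, with coverage unchanged.

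**Sensitivity to the planning rates.** Background (Section 3) says the true hypoxia rate "ranges from 1% to 70% in the literature". Control rates of 11.2% to 16.9%, taken from the sleep-apnea score study cited there, with 1.8% under CPAP, give 109 × 0.130 = 14 to 109 × 0.187 = 20 events. No treatment effect at 13.5% gives 109 × 0.270 = 29. The 32% and 18% quoted from the capnography study would give 109 × 0.50 = 55. Background also lists the German study's two rates in the opposite order to Section 7. The total is the same either way, but the two passages should be reconciled.

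**The case against.** A reader might infer that the stated analysis will fail in about 14% of trials because the CPAP arm may have no events. The documents do not support that. Section 7 describes a regression on demographic information, and arm is not demographic; its effect is tested by Fisher's exact test, which copes with an empty cell. A model of a few common demographic factors almost never fails. Where arm is added and separates, the damage is mostly confined to its own coefficient.

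A reader might also infer that leaving arm out spoils the demographic estimates. It does not. Arm is randomised, so omission brings no confounding and only slight attenuation, as the 0.391 against 0.40 shows.

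Three further points are fair. The covariate sets above are illustrative, and the plan may intend one factor at a time. Recruitment directed towards patients with OSA or a BMI of 30 or more (Section 4) could raise the event count above 17. And Firth's method cannot cure imprecision caused by few events.

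What stands is narrower. The event count is low on the plan's own figures. No covariate list rules out sparse categories. Nothing is specified for the case where a fit does not converge.

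**Conclusion.** The point holds as a minor improvement. On the plan's rates the demographic regression has about 17 events (about 18 with all 240). Maximum likelihood is serviceable for a few common factors without arm: about 0.1% to 0.5% failures, nominal coverage, wide intervals. It becomes fragile with a sparse category (about 18% failures at an assumed 10% prevalence) or with arm added (about 13% to 15%, mainly affecting the arm coefficient). Firth estimation removes the non-convergence and lowers root mean square error by about 3% to 12%.

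The event count follows directly from Section 7. The failure rates and error reductions depend on assumed covariates, prevalences and effects, and would ease if events are more frequent than planned. The primary analysis and the sample size are not affected.

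**What to change.** In Section 7, item b, state that the demographic model will be fitted by Firth penalised-likelihood logistic regression with profile-likelihood confidence intervals. Randomised arm can then be included as a term without risk of an infinite estimate. This is an option and not a correction, since omitting arm does little harm.

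It would also help to name a short list of factors in advance (for example BMI and OSA, which the protocol already highlights), say whether arm is in the model, and label the analysis exploratory. These are requests for specification only.

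The cost is a few lines of text and an add-on command in the statistical package already named. Coefficients are shrunk slightly, and a short list means fewer factors examined together. No extra patients, visits or data are needed.
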